## 2 BACKGROUND

Valvular heart disease is responsible for nearly 93,000 valve related operations and 20,000 deaths each year in the United States. It is also a contributing factor for another 42,000 deaths each year. The majority of these cases involve disorders of the aortic valve (63%). Specific aortic valvular disorders include: aortic stenosis, aortic regurgitation, or a combination of the two, with aortic stenosis being the leading indication for aortic valve replacement in adults.

The most common cause of aortic stenosis in adults is an idiopathic degenerative calcification process that produces an immobilization of the aortic valve cusps. This disease progresses from the base of the cusps to the free edge, eventually causing a reduction in the effective valve area. Other causes include a congenital malformation (often a bicuspid valve) and rheumatic fever. Classic symptoms of aortic stenosis include angina, syncope, dyspnea, heart murmur, fatigue, and heart failure.

Common causes of aortic valve regurgitation include idiopathic aortic dilatation, congenital abnormalities (bicuspid valve), degenerative calcification, rheumatic fever, infective endocarditis, systemic hypertension, dissection of the ascending aorta, Marfan's syndrome, and many others that occur much less frequently. Symptoms of aortic regurgitation include: angina, syncope, dyspnea, heart murmur, fatigue, and heart failure.

Patients with either aortic stenosis, regurgitation, or both may remain asymptomatic for many years however, after the onset of symptoms (angina, syncope, or dyspnea); the average survival is less than two to three years. Aortic valve replacement (AVR) appears to be the only effective treatment for these patients. For certain patients with severe aortic regurgitation who are not considered good surgical candidates, therapy with vasodilating agents may provide some benefit.

Presently, there are two broad categories of aortic valve prostheses; mechanical and tissue (bioprosthetic). The ball and cage, tilting-disc, and bileaflet are the three basic types of mechanical valve prostheses available today. There is a wide variety of bioprostheses available including: autografts (a valve moved from one anatomical position to another within the same individual), homografts/allografts (human valves or tissue taken from cadavers), and heterografts/xenografts (valves or tissue taken from animals). There are currently several different heterografts available. Heterografts are primarily constructed from porcine aortic valves that have been preserved and sewn onto a frame (stented) or left intact (stentless). A stented bovine pericardial valve is another type of commonly accepted heterograft.

Each valve type, mechanical or tissue, has associated risks and benefits. Mechanical valves are associated with potential lifetime durability but require long-term anticoagulation therapy. Tissue valves are reported to have reduced device durability, but typically do not require long-term anticoagulation therapy and are therefore associated with lower incidence of thromboembolic and hemorrhagic events. Implanting physicians must not only consider the various valve characteristics when deciding which aortic prosthesis to implant, but also various patient factors including, but not limited to age, coexisting medical conditions, anticoagulation therapy tolerance, and cardiac physiology.

### **3 OBJECTIVES**

#### **3.1 PRIMARY OBJECTIVE**

- 3.1.1 The primary objective of this investigation is to evaluate the long-term durability of the Trifecta valve.

#### **3.2 SECONDARY OBJECTIVES**

- 3.2.1 The secondary objectives of this investigation are to evaluate valve-related complications in the long-term.

### **4 ENDPOINTS**

#### **4.1 PRIMARY ENDPOINT**

- 4.1.1 Actuarial freedom from reoperation due to Structural Valve Deterioration (SVD) at year 10 post implant for patients who have the Trifecta valve implanted.

#### **4.2 SECONDARY ENDPOINTS**

- 4.2.1 The secondary endpoints of this investigation are:
  - 4.2.1.1 Actuarial survival rate;
  - 4.2.1.2 Freedom from valve related death;
  - 4.2.1.3 Freedom from structural valve deterioration.

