## **8 STATISTICAL ANALYSIS PLAN**

### **8.1 SAMPLE SIZE JUSTIFICATION**

- 8.1.1 The sample size estimation is based on the primary endpoint of this study, freedom from reoperation due to SVD at year 10 post implant for patients who have the Trifecta valve implanted.
- 8.1.2 It is assumed that the expected freedom rate from reoperation due to SVD at year 10 post implant will be  $96.5\% \pm 1.52\%$ , in order to establish a one side 95% confidence interval for the freedom rate with the lower bound as 94%, the required number of patients at risk at year 10 post implant is at least 142 using non-parametric survival analysis with Peto's variance. Assuming the overall mortality rate will be 39.50% at year 5 and 63.4% at year 10, the minimum sample size is 641 patients.
- 8.1.3 With 20% drop out rate, in total at least 801 patients need to be recruited.
- 8.1.4 Taking into account the effect of learning curve of the surgeons, the first 3 patients implanted by each surgeon without any experience with the Trifecta valve are not counted as part of the sample size.

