### **8.3 ADDITIONAL DATA**

- 8.3.1 For the time to event data, survival analysis will be used to estimate the survival rate and 95% confidence interval, and a Kaplan Meier curve will also be presented.
- 8.3.2 Continuous data will be summarized with mean, standard deviation, median and range. Frequency and percentage will be reported for all categorical data.

---

 Reference : Alan B cantor , SAS survival analysis techniques for medical research

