## 9.3 Patient Death

### 9.3.1 Procedure for Recording and Reporting Patient Death

9.3.1.1 Safety surveillance and reporting will be done for all patients enrolled in the investigation.

9.3.1.2 Safety surveillance and reporting starts at the time when the patient is enrolled into the investigation (date of signature of the informed consent) until the last investigational visit has been performed.

9.3.1.2.1 All **Patient Deaths** are to be documented and reported to the sponsor **immediately**.

9.3.1.3 Should death occur, record death information in the hospital records, **immediately** document the information in the Death case report form (CRF). By completing the CRF the sponsor will be notified.

9.3.1.3.1 Refer to appendices "Data Collection" and "Data Collection Method".

9.3.1.3.2 Access the eCRF application.

9.3.1.3.3 Select the visit the patient death is related to or indicate it as visit unscheduled visit.

9.3.1.3.4 Enter patient death information into the Patient Death CRF.

- Date the death occurred;
- Date the center investigator or delegate became aware of the death;
- Place where death occurred (e.g. hospital, nursing home, patient's home);
- If death was witnessed;
- If autopsy was performed;
- If the Trifecta Valve was returned to SJM? If not, reason should be specified.
- Temporal cause of death
- Primary cause of death including if death was caused by valve-related complications (hemolysis, bleeding event, structural valve deterioration, endocarditis, non-structural dysfunction, valve reoperation, embolism, sudden unexplained, valve thrombosis)
- Details regarding death; and
- If details of serious adverse event associated to the death are known by the center/investigator/delegate.

9.3.1.3.5 The CRF must be authorized by the principal investigator or delegated co-investigator.

9.3.1.3.6 Submit the CRF. When the CRF is submitted, an alert is generated notifying the sponsor.

- 9.3.1.4 Patient death may be an outcome of a serious adverse event (SAE). If the death is related to a SAE, all the efforts to get SAE details should be made and the Adverse Event CRF must be completed.
- 9.3.1.5 Patient death is an early conclusion to the patient's participation in the investigation. Complete Termination CRF.
- 9.3.1.6 The investigator must notify the EC or IRB, if appropriate, in accordance with national and local laws and regulations.

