## 9.9 PROTOCOL REQUIRED FOLLOW-UP

- 9.9.1 Scheduled visits will occur yearly over 10 years after the implant date. The follow up will occur in the outpatient department of each participating institution or, if not possible, by telephone contact with the patient.
- 9.9.2 The Follow Up schedule is summarized in Table 1.
- 9.9.3 The following information will be collected at the follow up visit either from hospital records or through patient interaction (documented in the hospital records):
  - 9.9.3.1 Provide the most recent value (within the last month) of the New York Heart Association (NYHA) classification;
  - 9.9.3.2 Patient Cardiac Current Medication
    - Provide information on cardiac medication therapy.;
  - 9.9.3.3 Echocardiography (if available)
    - Provide follow-up echo data (echo date must be in the follow-up window);
- 9.9.4 Record the follow up information in the hospital records and complete the Follow Up Case Report Form (CRF).
- 9.9.5 Adverse Event (when applicable)
  - 9.9.5.1 Check with the patient if any adverse events or adverse device effect occurred since the last visit and document this in the hospital records.
  - 9.9.5.2 Report the adverse event according to specifications in section "Adverse Event" of the Case Report Form (CRF).
- 9.9.6 Patient Death (when applicable)
  - 9.9.6.1 If the patient died before the visit took place, report it immediately to the sponsor as indicated in section "Patient Death".
- 9.9.7 Early Withdrawal (when applicable)
  - 9.9.7.1 If the patient decides to withdraw from the investigation for whatever reason, report this immediately to the sponsor as indicated in section "Early conclusion to patient participation".
- 9.9.8 Refer to "Appendix Data Collection" for access and information regarding patient data collected for this investigation.

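### No competing-risk method is planned for freedom from valve-related death: under the Kaplan-Meier default, 1-KM exceeds the proportion of patients dying of that cause

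*Combined protocol and SAP*

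**What the plan says.** Section 4.2.1.2 names the endpoint as "Freedom from valve related death" and defines it no further. The word actuarial is attached to the primary endpoint (4.1.1) and to overall survival (4.2.1.1), but not to this endpoint or to freedom from structural valve deterioration, SVD (4.2.1.3).

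No analysis is given for it by name. Section 8.3.1 is generic: "For the time to event data, survival analysis will be used to estimate the survival rate and 95% confidence interval". The same item promises a Kaplan-Meier plot for these data. Nothing in section 8 says how a non-valve death enters the analysis of a single cause of death, and no cumulative-incidence or other competing-risk method appears.

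Three other places bear on the point:

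- Section 8.1.2 sets the mortality level: "Assuming the overall mortality rate will be 39.50% at year 5 and 63.4% at year 10".
- Section 9.9.1 sets the horizon: "Scheduled visits will occur yearly over 10 years after the implant date".
- Section 9.3.1.3.4 shows that the Death CRF records "Primary cause of death including if death was caused by valve-related complications".

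**The concern.** For valve-related death, a death from any other cause is a competing event: once it has happened, the endpoint can no longer occur. A Kaplan-Meier curve for one cause, run in the usual way, treats those patients as censored. It then estimates the risk that would apply if nobody died of anything else. That is a legitimate net quantity, but it is not the proportion of patients who die of the valve.

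When few patients die of other causes the two nearly coincide. Here the plan expects most patients to have died by year 10. A reader who takes 1 minus the reported freedom as the proportion dying of the valve would get too high a figure, to the device's disadvantage. Adding it to the matching figure for other deaths would give more than all-cause mortality.

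**Working it through.** **The plan's mortality input.** Survival is 1 - 0.395 = 0.605 at year 5 and 1 - 0.634 = 0.366 at year 10. Since 0.605² = 0.366, the two figures fit one constant hazard with 63.4% read as cumulative. The plan's sample size reproduces as 142 / (0.605 × 0.366) = 641.3, and 641 / 0.8 = 801.25. No figure is stated for valve-related death.

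**Direction.** Cumulative incidence weights the valve-death hazard at each time by all-cause survival. 1-KM weights the same hazard by survival from valve death alone, which is never smaller. So 1-KM cannot fall below the cumulative incidence.

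**Size with a constant share.** Let f be the valve-related share of the death hazard. The documents do not give f, so 5% to 30% is an assumption. At year 10:

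- cumulative incidence = f × 0.634
- 1-KM for valve death = 1 - 0.366^f
- 1-KM for non-valve death = 1 - 0.366^(1-f)

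| f (assumed) | Cumulative incidence | 1-KM | Ratio | Excess (points) | Valve + non-valve 1-KM |
|---|---|---|---|---|---|
| 5% | 3.2% | 4.9% | 1.55 | 1.7 | 66.4% |
| 10% | 6.3% | 9.6% | 1.51 | 3.2 | 69.1% |
| 20% | 12.7% | 18.2% | 1.44 | 5.5 | 73.5% |
| 30% | 19.0% | 26.0% | 1.37 | 7.0 | 76.6% |

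The last column compares with 63.4% all-cause. Its surplus equals the product of the two 1-KM values; at f = 20%, 0.182 × 0.553 = 0.101, and 63.4% + 10.1% = 73.5%.

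**Timing.** Hold the total hazard constant and let the valve share change over time. These patterns are illustrations, not bounds.

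- Share 50% in years 0-2, then none: cumulative incidence 0.5 × 18.2% = 9.1%; 1-KM 9.6%; ratio 1.05.
- Share 60% in year 0-1, then 10%: cumulative incidence 0.6 × 9.6% + 0.1 × (63.4% - 9.6%) = 11.1%; 1-KM 14.0%; ratio 1.26.
- Share 5% in years 0-5, then 35%: cumulative incidence 0.05 × 39.5% + 0.35 × (63.4% - 39.5%) = 10.3%; 1-KM 18.2%; ratio 1.76.

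**Earlier horizon.** At year 5, with 39.5% mortality, constant shares of 10% and 30% give 4.9% against 3.95% (ratio 1.24) and 14.0% against 11.85% (ratio 1.18).

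**Reading of 63.4%.** The 641 multiplies the two survival figures together, as if 63.4% were conditional on surviving to year 5. On that reading cumulative mortality would be 1 - 0.605 × 0.366 = 77.9%, and the ratio would be 1.80 at a 10% share and 1.61 at 25%. The main table uses the cumulative reading, which gives the smaller effect.

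**The case against.** Four points can fairly be made against this.

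- **Kaplan-Meier may be what is wanted.** If other deaths are independent of valve deaths, 1-KM is a valid net risk. The secondary objective (3.2.1) concerns valve-related complications, which suits a device-focused quantity. The missing word actuarial settles little, since freedom from SVD lacks it too. This stands: 1-KM is too high only as an estimate of the proportion of patients dying of the valve, and the plan does not say which quantity it means. Independence cannot be checked from the data.
- **Section 8.3.1 states no censoring rule.** A reader might infer that the plan prescribes censoring of non-valve deaths. It does not; that is the default behaviour of the method named. The gap is an unstated rule for competing deaths.
- **Sums above all-cause mortality are a known property of net estimates.** True, and not an error in themselves. They do show that these figures cannot be read as proportions of patients. No table placing them beside overall survival is specified.
- **Little hangs on it.** The 94% threshold belongs to the primary endpoint. No hypothesis or decision attaches to valve-related death, and the default reading would not flatter the device. This stands and limits the weight of the point.

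**Conclusion.** The plan leaves the handling of non-valve deaths unspecified for an endpoint where, on its own mortality assumption, it makes a visible difference. Under the default, 1-KM at year 10 is about 1.4 to 1.55 times the cumulative incidence, or about 2 to 7 percentage points higher. That rests on a constant valve-related share of 5% to 30% and on 63.4% being cumulative.

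A reader might infer a fixed overstatement of 40% to 50%. The documents do not support that. It would need a constant share of about 11% to 25%, and they give neither the share nor the timing of valve deaths. The timing patterns tried gave excesses from about 5% to 76%. The direction does not depend on these assumptions; the size does.

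This is a worthwhile improvement to the reporting of a secondary endpoint. It does not call the primary analysis into question.

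**What to change.** In section 8.3.1:

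- Estimate valve-related death by the Aalen-Johansen cumulative incidence, with non-valve death as the competing event and a 95% confidence interval. Show it with the cumulative incidence of non-valve death, so that the two sum to all-cause mortality.
- Keep the Kaplan-Meier figure, labelled as actuarial (net), for comparison with earlier series, and state that non-valve deaths are censored in it.
- Freedom from SVD (4.2.1.3) faces the same competing deaths under the same sentence; give a cumulative incidence beside its actuarial figure.
- Leave the primary endpoint and its 94% bound unchanged.

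The cost is a few lines of SAP text and a standard software option. Cause of death is already on the Death CRF, so no new data, visits or patients are needed. The downside is that two related figures need a line of explanation.

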## **5 PATIENT SELECTION CRITERIA**

### **5.1 PATIENT ENROLLMENT**

A patient who meets all the inclusion criteria and does not meet any of the exclusion criteria is eligible to participate in the investigation. A patient is enrolled in the investigation only when s/he has provided written informed consent. Once enrolled, a patient is expected to comply with the scheduled visits and required activities according to the protocol.

### **5.2 INCLUSION CRITERIA**

- 5.2.1 Patients implanted for less than 9 months, or candidate for implantation with a St Jude Medical Trifecta valve, as per current guidelines;
- 5.2.2 Patient requires aortic valve replacement. (Note: patients undergoing concomitant procedures, e.g. coronary artery bypass grafting, supracoronary replacement of ascending aorta, mitral valve repair, tricuspid valve repair, atrial fibrillation ablation, patients that had previous aortic valve replacement or CABGs are eligible for this study).
- 5.2.3 Patient is legal age in host country.
- 5.2.4 Patients must be able and willing to provide written informed consent to participate in this investigation; and
- 5.2.5 Patients must be willing and able to comply with all follow-up requirements.

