### **6.2 DURATION**

- 6.2.1 The first enrollment is anticipated in 2010.
- 6.2.2 The enrollment period will be approximately 15 months.
- 6.2.3 The patient will participate in this investigation for approximately 10 years from enrollment to the last follow-up.
- 6.2.4 The patient may withdraw from the investigation at any time, for any reason. In this case, the procedures for reporting should be followed as mentioned in the section 0 Early Conclusion to Patient Participation.

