### 7.1.1 The Trifecta valve:

The Trifecta valve is a tri-leaflet stented pericardial valve designed for supra-annular placement in the aortic position. The valve is fabricated using a polyester-covered titanium stent. The stent, excluding the sewing cuff, is then covered with porcine pericardial tissue. This covering minimizes mechanical wear by allowing only tissue-to-tissue contact during valve function. A silicone insert within the polyester sewing cuff is contoured to conform to the shape of the native annulus. The valve leaflets are fabricated from bovine pericardium. The porcine and bovine pericardium are preserved and crosslinked in glutaraldehyde. Glutaraldehyde, formaldehyde, and ethanol are used in the valve sterilization process. The Trifecta valve is processed using Linx™ anti-calcification technology. The Trifecta valve received CE mark in March 2010.

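### Patients may enrol up to 9 months after implant, but Section 8 has no delayed-entry rule: an ordinary Kaplan-Meier from implant overstates survival and, usually less, freedom from valve-related death

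*Combined protocol and SAP*

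**What the plan says.** - **Who may enter.** 5.2.1 accepts "Patients implanted for less than 9 months, or candidate for implantation with a St Jude Medical Trifecta valve". Under 5.1, "A patient is enrolled in the investigation only when s/he has provided written informed consent".
- **When deaths start to count.** 9.3.1.2 starts safety and death surveillance on the date the consent form is signed.
- **Clock.** 8.2.1 times the primary endpoint in days from implant, and 9.9.1 schedules the yearly visits from implant. Section 6.2 counts from enrolment instead: "The patient will participate in this investigation for approximately 10 years from enrollment to the last follow-up".
- **Affected endpoints.** 4.2.1 lists three secondary endpoints. Two concern death: the actuarial survival rate and "Freedom from valve related death".
- **Their analysis.** 8.3.1 provides survival analysis, a 95% confidence interval and a Kaplan-Meier curve. It gives no time origin and no rule for patients who enter after time zero.
- **Figures used below.** Mortality in 8.1.2: "Assuming the overall mortality rate will be 39.50% at year 5 and 63.4% at year 10". Dates: "The Trifecta valve received CE mark in March 2010" (7.1.1), "The first enrollment is anticipated in 2010" and "The enrollment period will be approximately 15 months" (6.2).

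**The concern.** A patient enrolled some months after implant had to survive those months in order to consent. Patients who died in the same interval can never join the cohort. With implant as time zero, an ordinary Kaplan-Meier places late entrants in the risk set from day 0, so the denominator includes people who could not contribute a death. The early hazard is diluted, and the lost deaths are never recovered later on the curve. The bias is upward for any late share above zero, which favours the device.

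At stake are two of the three secondary endpoints and the nominal 95% intervals that 8.3.1 promises. The relative error is largest against the sampling error in the first years. No decision criterion rests on these endpoints, so the harm is to the reported survival curves and not to the 94% criterion.

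**Working it through.** **Plan figures first.** The documents state no figure for this bias, but the sample-size chain reproduces. With Peto's variance, 0.965² × 0.035 / 0.0152² = 141.1, rounded up to 142. Then 142 / (0.605 × 0.366) = 641.3 and 641 / 0.80 = 801.25. None of this changes with delayed entry.

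**Hazard of death.** From 8.1.2, survival is 60.5% at year 5 and 36.6% at year 10. −ln(0.605)/5 = 0.1005 and −ln(0.366)/10 = 0.1005 per year, so a constant hazard h = 0.1005 fits both points. S(t) = 0.904, 0.605 and 0.366 at years 1, 5 and 10.

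**(1) Uniform entry over months 0 to 9.** Let p be the late share (an assumption). Beyond 9 months the ordinary Kaplan-Meier tends to S(t) × [(1 − p) + p × E(1/S(a))], where a is the entry time. The bias is therefore

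p × S(t) × [(e^(0.75h) − 1)/(0.75h) − 1] = p × S(t) × 0.0387.

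| Late share | Year 1 | Year 5 | Year 10 | Coverage of 95% interval, years 1 / 5 / 10 |
|---|---|---|---|---|
| 25% | +0.87 | +0.58 | +0.35 | 82 / 94 / 94% |
| 50% | +1.75 | +1.17 | +0.71 | 54 / 89 / 93% |
| 75% | +2.62 | +1.75 | +1.06 | 19 / 82 / 91% |

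Bias is in percentage points. Coverage comes from 4,000 simulated trials with N = 801, 20% dropout over 10 years and Greenwood intervals.

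**(2) Back-fill bounded by the plan's dates.** Suppose implants run steadily from CE mark, the study opens M years later, every survivor is enrolled at opening, and the following 1.25 years (15 months) enrol before implant. Survivors at opening are A = (1 − e^(−hM))/h in units of one year's implants. The late share is A/(A + 1.25) and the bias is share × S(t) × (M/A − 1).

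| Opening after CE mark | Late share | Year 1 | Year 5 | Year 10 | Coverage, year 1 |
|---|---|---|---|---|---|
| 3 months | 16.5% | +0.19 | +0.13 | +0.08 | 94% |
| 6 months | 28.1% | +0.64 | +0.43 | +0.26 | 89% |
| 9 months | 36.6% | +1.26 | +0.85 | +0.51 | 71% |

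**(3) Freedom from valve-related death.** Take a constant fraction f of deaths as valve-related (an assumption), with other deaths censored. The observed valve-related hazard is f × h times the part of the ordinary risk set that is truly under observation. With p = 50% and f = 10/20/30%, the bias is +0.19/+0.38/+0.56 at year 1 (0.6 to 1.0 standard deviations of the estimate), +0.18/+0.35/+0.50 at year 5 and +0.17/+0.31/+0.43 at year 10. Under scenario (2) with f = 10 to 30%, it runs from +0.02 to +0.40 at year 1 and from +0.02 to +0.31 at year 10.

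**Higher early mortality.** With an assumed extra 3% mortality in the first 30 days, and the year-5 and year-10 values kept, uniform entry overstates year-1 survival by 1.47 points at p = 25% and 2.94 at p = 50%.

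**Primary endpoint.** The reoperation hazard is −ln(0.965)/10 = 0.00356 per year. If every patient entered at 9 months the bias would be 96.5 × (e^(0.75 × 0.00356) − 1) = 0.26 points; at p = 50% with uniform entry it is 0.06. The plan's standard error is 1.52 points.

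**With delayed entry.** In the same simulations, coverage is 94.4 to 95.5% and bias is within 0.06 points in every scenario.

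**The case against.** The strongest reply is that the bias is conditional and, on the evidence in the documents, modest.

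- **Origin.** Implant is the stated origin only for the primary endpoint, where the effect is negligible. For the death endpoints it is inferred from 8.2.1 and 9.9.1. This stands as a condition. The other reading does not remove the need for a rule, because a curve from enrolment would mix patients at different times since implant.
- **Late share.** Most of the text describes enrolment before surgery (5.2.2, 5.3.5, Table 1, 9.7.1). Nothing supports a late share of 50 or 75%, and the worst coverage figures come only from those. This stands, so scenario (2) is the better guide. It is not a strict ceiling: it assumes every survivor is enrolled, which raises the share, but it leaves out post-implant enrolment after opening, which 5.2.1 allows.
- **Long-term aims.** The objectives are long-term and the year-10 effect is small. This stands. If the 641 is taken to imply 10-year survival of 0.605 × 0.366 = 22.1%, the year-10 figures in (1) fall further, to 0.21/0.43/0.64.
- **Ranking.** Valve-related death need not be less affected in absolute points. With p = 50%, an extra 6% early mortality, and 60% of early but 10% of later deaths valve-related, the year-10 bias is 2.43 points against 1.76 for survival. The direction and the remedy are unchanged.

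**Conclusion.** The concern holds. Timed from implant and analysed with an ordinary Kaplan-Meier, actuarial survival and freedom from valve-related death are both overstated whenever any patient enrols after implant. Under the plan's mortality, survival is too high by about 0.2 to 1.3 points at year 1 and 0.1 to 0.5 at year 10 in the back-fill scenario, with year-1 coverage between 94% and 71%. Larger late shares make it worse.

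The size rests on three things that the documents do not settle: the late share and entry times, the valve-related share of deaths, and early mortality. Operative deaths could make early mortality higher than the constant hazard. The exclusions in 5.3 (life expectancy under two years, dialysis, ejection fraction below 25%) could make it lower. The primary endpoint, the 94% criterion and the sample size are essentially untouched. This should be corrected, but it does not threaten the study's main conclusion.

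**What to change.** In 8.3:

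1. State the implant date as the time origin for actuarial survival and freedom from valve-related death.
2. Enter each patient enrolled after implant into the risk set at the consent date (delayed entry).
3. Report how many patients enrolled after implant, with their implant-to-consent times.
4. Add a sensitivity analysis restricted to patients who consented before implant. Delayed entry does not correct for sites choosing healthier survivors.

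Delayed entry for the structural valve deterioration endpoints and the Cox model is optional, as a sensitivity analysis.

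As a separate item, reconcile 9.7.1 (baseline after enrolment and within 30 days before surgery) with 5.2.1, since a patient enrolled after implant cannot meet both. Also confirm that baseline NYHA class for these patients is the pre-operative value, as Table 1 implies.

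**Cost.** SAP wording and one entry-time variable; consent date defines enrolment and 8.2.1 already uses the implant date. Early risk sets shrink, so early intervals widen. In simulation at N = 801, the standard deviation of year-1 survival rises from 1.00 to 1.10 points at 25% late and from 0.93 to 1.15 at 50% late. At year 10 it is unchanged (1.81 against 1.80). The method needs enough patients consented before implant to form an early risk set.
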